1. RESEARCH QUESTIONS

1.1. OVERVIEW OF RESEARCH QUESTIONS

Please state the research question(s) that the evaluation intends to answer and for each research question indicate the type: implementation or outcome.

- *Implementation Questions: Identifying whether a program has been successful in attaining desired implementation goals (e.g., reaching intended target population, enrolling intended number of participants, delivering training and services in manner intended, etc.)*
- *Outcome Questions: Identifying whether program is associated with intended outcomes for participants (e.g., do participants' knowledge, attitudes, behaviors, or awareness change?)*

Research questions in this study are framed by a Random Control Trial (RCT) design that will be used to determine if *TCD Project* participants who receive *enhanced TCD services* (treatment) derive more benefits than those who receive only *standard TCD services* (control), and they guide two types of analyses in this study—impact and implementation (see Table 1.1 below). Impact analyses estimate the primary benefits of participation for different service conditions six months after TCD enrollment. Primary benefits refer to outcomes that indicate improved attitudes and behavior for healthy

family relationships (parent, co-parent, and partner). However, strong conclusions can only be drawn about the benefits of participation when impact estimates are made after full or nearly full implementation of TCD services. Conclusions are more difficult to draw for impact estimates that are made when participants do not receive the intended service amounts. Consequently, implementation analyses place impact estimates in the appropriate context for interpretation by considering the extent to which TCD services are fully implemented for participants in both study groups.

Table 1.1: Research questions by type for the impact study, implementation and outcome

No	Research Question	Implementation or Outcome?
I1	To what extent were the enrollment targets for the TCD Project achieved for the treatment and control groups?	Implementation
I2	To what extent were the intended amounts of standard TCD services (TYRO Dads, Core Communication curricula) offered to and received by the control group?	Implementation
I3	To what extent were the intended amounts of enhanced TCD services (TYRO Dads, Core Communication, Ray of Hope curricula) offered to and received by the treatment group?	Implementation

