- **Goal 2 - Deliver enhanced TCD services to the Treatment Group:** Candidates randomly assigned to the treatment group will understand they receive *enhanced TCD services* to develop their skills to engage in healthy behaviors for parenting, co-parenting, partner relations, employment, financial management and address the dynamics of domestic violence, but only after receiving an orientation about the TCD Project and giving project staff informed consent to participate in study activities. Then, the *Ray of Hope* curriculum will be delivered only to the treatment group as well as the *TYRO Dads* and *Core Communication* curricula and support services through case management the *ASF Mini-Clinic*, as needed, under a shared condition with the control group.
- **Goal 3 - Conduct Continuous Quality Improvement (CQI) to ensure full implementation of *standard* and *enhanced TCD services* for study groups:** Reports prepared and presented to the CQI Team by evaluators will use a series of performance indicators to track key outputs over time to identify any *TCD services* delivered to study groups that might fall short of the intended amounts to be offered (i.e., fidelity standards) and received (i.e., dosage thresholds) by them. The CQI Team will then work with project staff to develop and implement performance interventions to address any outputs that need improvement to ensure the services offered to and received by participants meet the intended amounts by the end of each program year.

Desired Outcomes: Outcomes specified in the logic model theorize the primary outcomes that are desired for participants in each study group after they receive either *standard* or *enhanced TCD services*. All outcomes specified in the logic model are theorized to be more positive for parents assigned to the treatment group because they receive *enhanced TCD services*, whereas the control group receives *standard TCD services*.

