For the implementation analysis, program fidelity will be descriptively reported by the percentage of enrolled participants who receive: 1) any primary workshops, 2) employment supports, 3) substantive service contacts, 4) referrals. The program aims to provide all participants each of these four program components, so the percentage of participants who receive each of these will be compared to the 100% benchmark. Number of substantive service contacts per participant will also be compared to the benchmark of 8 SSCs set by OFA for FIRE grantees.

Dosage will be measured by percent of target primary workshops participants attend on average (using 90% as a benchmark), and categories of attendance (initial, halfway, 90%, 100%) will be reported and compared to targets established by the program.

Handling missing data

Outcomes

When creating the composite measures for our behavior and attitude outcomes, we will create a composite score by taking the average of multiple individual items. For these measures, our current plan is to use 20% as a threshold for allowable missing items, based on guidance from evaluation technical assistance resources. This plan is contingent on the final distribution of missing data in our data set. If participants have more than 20% of items missing for a given construct, the respondent will be assigned a missing value for that construct and will be excluded from the analytic sample for that outcome. We will not be imputing truly missing values for outcomes. To create a construct score, the average will divide by the number of non-missing values in the construct.

For outcomes that use single survey items, participants who do not respond to that item on either the pre- or follow-up survey will be excluded from the analytic sample for that outcome.

Data for the implementation outcomes could be missing as a result of programmatic data entry issues. For the sake of this evaluation, we assume that any primary or support services received by a participant are being accurately logged into nFORM, so a lack of documented attendance, service contacts, referrals, etc. is indicative of lack of services (i.e., a participant not receiving the program components as intended).

Assessing non-response bias

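### The SAP plans no measure of service offered, so the offered half of implementation questions I2 and I3 has no specified analysis, for Ray of Hope in particular

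*SAP*

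**What the plan says.** **Protocol.** Under Goal 3 of section 3 (Logic Model), reports to the quality improvement team are to identify services that "fall short of the intended amounts to be offered (i.e., fidelity standards) and received (i.e., dosage thresholds) by them". Fidelity is thus an amount offered and dosage an amount received. Table 1.1 in section 1.1 keeps both. I2 asks how far the intended standard services were "offered to and received by the control group". I3 asks how far the intended enhanced services, which add Ray of Hope, were "offered to and received by the treatment group". Goals 2 and 3 in section 2 (Evaluation Goals) say the same. Section 1.2 gives Ray of Hope as 10 hours.

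**SAP, section 1, implementation analysis.** Here "program fidelity will be descriptively reported by the percentage of enrolled participants who receive: 1) any primary workshops", and likewise for employment supports, service contacts and referrals, and "the percentage of participants who receive each of these will be compared to the 100% benchmark". In addition, "Number of substantive service contacts per participant will also be compared to the benchmark of 8 SSCs set by OFA for FIRE grantees". Dosage is the mean percent of target primary workshops attended, with a 90% benchmark, plus attendance categories (initial, halfway, 90%, 100%). The missing-data text takes the absence of a documented service to mean that the service was not received.

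**The concern.** The SAP uses the word fidelity for a different quantity from the one the protocol defines. Its fidelity and dosage measures all start from what a father received; none starts from what was held for him. For workshops, one attendance is enough to count.

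This matters because section 1.1 of the protocol uses the implementation results to decide how firmly the impact estimates can be read. If R1 to R4 show no difference, there are two quite different explanations: Ray of Hope was not delivered in the intended amount, or it was delivered and fathers did not come. The SAP also attributes any benefit to the intervention on the ground that all other services are delivered alike to both arms. That is a statement about delivery, and the SAP tabulates nothing that would support it.

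**Working it through.** The plan gives no numerical result to reproduce, so the check has two parts.

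**1. Each SAP measure against the two quantities in the protocol**

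| SAP measure | Counts | Offered or received? |
|---|---|---|
| Any primary workshop, against 100% | Fathers with at least one attendance | Received |
| Employment supports, service contacts, referrals, each against 100% | Fathers who had each | Received |
| Service contacts per participant, against 8 | Contacts per father | Received |
| Percent of target workshops attended, against 90% | Attendance | Received |
| Attendance categories | Attendance | Received |

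None divides sessions or hours held by those intended. None is specified by study group or for Ray of Hope. A treatment-group father who attended one TYRO Dads session and no Ray of Hope session passes the workshop item.

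**2. How the workshop measures behave**

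Assumption: a target of T = 12 workshops, inferred from the incentive schedule (protocol section 9.4). The SAP gives no number. Formulas:
- offered = held / T
- workshop item = share of fathers with at least one attendance
- dosage = mean(attended / T)

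| Case | Offered | Workshop item | Dosage |
|---|---|---|---|
| A. 6 held, all fathers attend 6 | 6/12 = 50% | 100% | 6/12 = 50% |
| B. 12 held, all fathers attend 6 | 12/12 = 100% | 100% | 6/12 = 50% |
| C. 3 held, all fathers attend 3 | 3/12 = 25% | 100% | 3/12 = 25% |
| D. 6 held, 264 of 310 attend 6, 46 attend none | 6/12 = 50% | 264/310 = 85.2% | (264 × 6)/(310 × 12) = 42.6% |

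A and B agree on both SAP workshop measures, and on the attendance categories too, because every father attends exactly 6. The amount offered differs by 50 points. This does not depend on T: for any even T, half held and fully attended matches all held and half attended. Case D shows that the workshop item reaches 100% only if every enrolled father attends at least once.

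**Less uniform attendance.**
- Case E: 12 held, each attended independently with probability 0.58. Workshop item = 1 − 0.42^12 = 99.997%; dosage = 58%; offered = 100%.
- Case F: 7 held, all attended. Workshop item = 100%; dosage = 7/12 = 58.3%; offered = 58.3%.

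The workshop item and mean dosage agree to the nearest percent. The attendance categories do not. In E, Binomial(12, 0.58) puts 19.6% of fathers below halfway (5 or fewer) and 1.4% at 90% or more (11 or 12). In F both shares are 0%.

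**Meaning of target.** If it means the intended number, A shows 50% dosage and clearly misses 90%. If it means workshops actually held, A shows 6/6 = 100% and the shortfall disappears. The SAP does not say which is meant.

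**The case against.** Two stronger readings are tempting, and the documents support neither.

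- **That the amount offered is never measured.** The protocol's evaluation timeline has nFORM data collected to track delivery of intended amounts, and the logic model has quality improvement reports that follow amounts offered. What is missing is a specified SAP analysis, not the data.
- **That a shortened program would be reported as 100% fidelity.** SAP fidelity has four components plus the 8-contact benchmark. The 100% result concerns the workshop item alone, and only if every enrolled father attends once. A shortfall would also show in dosage against 90%, provided that target means the intended number.

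Other objections also carry weight. The attendance categories can separate some patterns, as E and F show, so it would be wrong to say that the full SAP output never distinguishes short delivery from low attendance. Both arms attend TYRO Dads and Core Communication together (protocol section 7), so a cancelled standard session affects both alike; the arm contrast depends on Ray of Hope delivery, which the 12-workshop example does not isolate. Section 1.1 speaks of services received when it says conclusions become harder to draw, and SAP dosage does address receipt. The measures are descriptive, and no confirmatory test depends on them.

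These points limit the consequence. They do not supply the missing measure. Categories of attendance are at best indirect evidence about delivery, and the focus on Ray of Hope makes its absence from the SAP text more important.

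**Conclusion.** The concern holds in this limited form. The SAP's use of fidelity conflicts with the protocol's definition. Followed as written, the SAP addresses the received half of I2 and I3 and has no planned analysis of the offered half. The workshop item does not respond to shortened delivery. Mean dosage cannot by itself tell under-delivery from under-attendance: in the example, the same 100% and 50% arise with 50% or 100% of workshops held.

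The size rests on an assumed 12 workshops and on simple attendance patterns, and it illustrates rather than predicts. The intended amounts for TYRO Dads and Core Communication could not be checked, because the logic model document that the protocol cites for dosage and schedule is not in the text available. The change should be made because it bears on how the impact results are read. It does not threaten the validity of the impact estimates.

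**What to change.** In the SAP's implementation analysis:

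1. Define fidelity as the logic model does: sessions or hours held for a father's cohort divided by those intended, compared with 100%. Report it by curriculum and study group, with Ray of Hope shown separately against the protocol's 10 hours.
2. Relabel receipt of any primary workshop as a receipt measure, under the initial attendance category that the SAP already lists.
3. Report attendance as a percent of intended and as a percent of offered amounts, and state that target means the intended number. In the example, A then reads 50% of intended and 100% of offered, and B reads 50% and 50%.

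The cost is SAP wording and one more tabulation, from delivery data that the protocol already plans to collect. The downside is that the reported fidelity figure may be less favourable. Randomization, sample size and the impact models do not change.

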Who will be responsible for monitoring random assignment compliance?	The CQI Data Manager is responsible for monitoring random assignment compliance by case managers during study enrollment under the guidance of other CQI Team members. The distribution of participants across study groups will be monitored by the CQI Team using the relevant operational reports on nFORM.
What methods will be used to monitor the comparability of the study groups?	nFORM data will be used to produce enrollments into study groups to assess their comparability. Baseline equivalency analyses will determine whether there are statistically significant differences between study groups.

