9.3. RCTS ONLY: POWER ANALYSIS

For each confirmatory outcome, please provide power analyses demonstrating proposed sample sizes will be able to detect expected effect sizes for the outcomes targeted. Refer to previous studies of similar interventions for estimates of the required sample to inform power analyses. Note: If an impact evaluation is not proposed, this issue does not need to be addressed. You may use the table below to report the assumptions used in your power calculations, as well as the resulting minimum detectable impact for your confirmatory outcomes or provide them in the space below.

	Outcome 1	Outcome 2	Outcome 3	Outcome 4
Outcome Name	Healthier Parenting Attitudes	Healthier Partner Relationship Behavior	Healthier Parenting Behavior	Healthier Co-Parenting Behavior
Continuous or binary?	continuous	continuous	continuous	continuous

Level of significance (e.g., 0.05 percent)	0.05	0.05	0.05	0.05
Number of sides of test (one- or two-tailed)	One-tailed	One-tailed	One-tailed	One-tailed
Power (e.g., 80 percent)	80%	80%	80%	80%
Total number of individuals in analytic sample	620	620	620	620
If binary, enter mean of outcome variable				
If continuous outcome, enter the standard deviation of the outcome (>0)				
Proportion of individual-level (or within-group) variance explained by covariates				
For cluster RCTs: intraclass correlation coefficient	N/A	N/A	N/A	N/A
For cluster RCTs: proportion of group-level variance of	N/A	N/A	N/A	N/A

outcome explained by covariates				
Minimum detectable impact				
Minimum detectable effect size	0.2	0.2	0.2	0.2

If you did not provide report your assumptions using the table above, please enter them here.

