Chi-Square and 2-sample t-tests assess baseline equivalency of study groups by analyzing pre-survey responses to items that describe the characteristics of participants and their developmental starting points before receiving TCD services. Participant characteristics—such as demographics, family structure, and socioeconomic background—are reported on the nFORM ACS Survey. Developmental starting points refer to the attitudes and behavior exhibited before TCD participation and are reported on the nFORM Community Fathers Entrance Survey and OLLE Pre-survey. Chi-Square tests are run for

categorical and dichotomous variables, such as relationship status (e.g., married, single, divorced) or whether a participant reports having a savings account (i.e., yes/no). Two-sample t-tests are run for interval and continuous variables, such as the number of children in a household, or levels of agreement with healthy parenting attitudes. Any differences detected across study groups are incorporated into the model as co-variates.

Study group assignment (1=treatment, 0=control) is repeatedly regressed against the dependent variables to model comparisons of outcomes constructs between study groups (see the table below). Co-variates specified in the model will control for the influence of any significant baseline differences between study groups that were detected in the baseline equivalency analyses for demographics, family structure, socioeconomic background, and developmental starting points.

Procedures to run the linear regression model rely on standard regression to model the influence of study group assignment on dependent variables. All dependent variables are continuous, such as when participants report how many hours they spend with their child or respond to multiple items in a scaled construct by indicating levels of agreement with statements about key parent attitudes.

Benefits of the Ray of Hope curriculum will confirm hypotheses if respondents assigned to the treatment group report greater improvements in outcomes ($p < .05$) than those in the control group for each outcome measure identified above.

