We will conduct response rate analysis for each primary outcome of interest to assess non-response bias and adjust for threats to internal validity. Using data from the Applicant Characteristics Survey, we will look at demographics (race, ethnicity, age, education level) and primary reason for joining the program among participants who fall into each of the following categories: 1) non-respondents who answered no surveys after the ACS, 2) respondents who completed a pre-survey only, and 3) respondents who completed both a pre- and follow-up survey (complete case). We will also look for differential response rates between the standard/control and enhanced/treatment groups.

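### The SAP specifies no comparison of the two arms' characteristics among the fathers analysed for each outcome, so equal response rates and balance at entry would not show that the compared groups are comparable

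*SAP*

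**What the plan says.** Three checks bear on comparability.

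1. **Baseline equivalence.** SAP, Analytic approach: "Chi-Square and 2-sample t-tests assess baseline equivalency of study groups by analyzing pre-survey responses to items". Differences found this way become model covariates. The sample is not named. Protocol 7.1 says "nFORM data will be used to produce enrollments into study groups to assess their comparability", and then mentions baseline equivalency analyses, again without naming a sample.
2. **Response categories.** SAP, Assessing non-response bias, looks at demographics and reason for joining in three categories: no survey after the applicant survey, pre-survey only, and "respondents who completed both a pre- and follow-up survey (complete case". No split by arm is stated.
3. **Response rates.** "We will also look for differential response rates between the standard/control and enhanced/treatment groups".

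The analysed samples are defined elsewhere in the SAP. The impact study sample needs an entrance survey plus an exit and/or follow-up survey. Parenting attitudes use the exit survey; the behaviour outcomes are assessed at the six-month follow-up. The three parenting measures are limited to fathers who saw the child in the past month. If more than 20% of a construct's items are missing, "the respondent will be assigned a missing value for that construct and will be excluded from the analytic sample for that outcome". Outcomes are not imputed.

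**The concern.** The non-response section aims to assess, for each primary outcome, threats to internal validity and to adjust for them. A difference between responders and non-responders that is the same in both arms does not by itself unbalance a randomised comparison. Losing different kinds of fathers in each arm does. Neither non-response check is specified to show that: one has no stated split by arm, and the other counts how many answered, not who.

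The adjustment depends on the same gap. Covariates enter the model only if the equivalence tests flag them, so the sample used for those tests decides whether imbalance created by attrition can be corrected. Such imbalance has a plausible route. Fathers learn their assignment at once (Protocol 7.1), only the treatment arm is offered the additional curriculum of 10 hours (Protocol 1.2), and exit surveys mainly reach completers present at the last session (Protocol 10.4).

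A report could then state balanced groups and equal response although the groups behind a given estimate differ.

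**Working it through.** **The plan's own figures.** Protocol 9.2 gives 443 randomised and 310 analysed per arm: 310/443 = 70.0% in each arm, so 30% lost and equal response assumed. Protocol 9.3 gives a one-tailed test, alpha 0.05, power 80%, 620 in total and a minimum detectable effect of 0.2. With an outcome SD of 1, the standard error of the difference is sqrt(2/310) = 0.0803, and (1.645 + 0.842) × 0.0803 = 0.1997. The stated figure reproduces.

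**Do the response categories match the outcome samples?**

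| Father | Response category | Analysed? |
|---|---|---|
| Pre and exit surveys, no follow-up | none of the three | yes, for parenting attitudes |
| Pre and follow-up, more than 20% of a construct's items missing | complete case | no, for that construct |
| Pre and follow-up, did not see child in past month | complete case | no, for the parenting measures |

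Survey completion therefore does not identify who is analysed.

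**Illustration (assumed inputs; the documents give none).** Half of fathers have a trait that worsens the outcome by 0.5 to 0.8 SD. There is no true effect and 310 are analysed per arm.

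Bias = difference in trait share among the analysed × trait effect. The false-positive rate is 1 − Φ(z_crit − bias/0.0803), with z_crit 1.645 at 0.05 and 2.394 at 0.05/6 = 0.0083.

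*Opposite-direction loss.* Treatment keeps 60% of fathers with the trait and 80% without; control keeps 80% and 60%.
- Response is 70% in each arm. Over both arms, response is also 70% with the trait and 70% without. Both non-response checks look clean.
- Trait share among the analysed: 0.60/1.40 = 42.9% against 0.80/1.40 = 57.1%, a difference of 14.3 points.
- Bias: 0.143 × 0.5 = 0.071 SD to 0.143 × 0.8 = 0.114 SD, or 36 to 57% of the 0.2 target.
- False-positive rate: 22.5 to 41.2% at 0.05; 6.6 to 16.6% at 0.05/6.

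*Milder loss.* Treatment 60% and 80%; control 70% and 70%.
- Response is again 70% in each arm. The unsplit table shows 65% with the trait and 75% without, exactly as if both arms had kept 65% and 75%, where bias is zero.
- Trait share: 42.9% against 50%. Bias: 0.036 to 0.057 SD.
- False-positive rate: 11.5 to 17.5% at 0.05; 2.6 to 4.6% at 0.05/6.
- A two-sided 5% test of 42.9% against 50% has standard error sqrt((0.429 × 0.571 + 0.5 × 0.5)/310) = 0.040, so z = 0.071/0.040 = 1.79 and power is about 43%.

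**Second model, by simulation.** 4,000 trials, 443 per arm, 70% responding in each. The assumed correlation of the baseline score with willingness to respond is +0.2 in one arm and −0.2 in the other, and the baseline-outcome correlation is 0.5. The analysed groups differ by 0.20 SD at baseline. Tests among all randomised fathers and of response rates are both clean in 90% of trials. A by-arm baseline test among the analysed flags the gap in 70%. The one-sided 5% false-positive rate is 34% without the baseline score as covariate and 5% with it.

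**The case against.** The strongest reply is that the SAP identifies the impact study sample before it describes the equivalence tests. Those tests may therefore be meant for that post-attrition sample, by arm, and they include baseline attitudes and behaviours. A reader might infer that the plan tests balance only at entry, or has no by-arm check after attrition. The documents support neither, because no sample is named. Even so, a sample requiring exit and/or follow-up mixes fathers who have only one of the two later surveys. It is not specific to any outcome, and item missingness and the child-contact restriction come on top.

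It is also fair that pooling of the arms in the response table is an inference, since the SAP does not say. The promise of an analysis for each primary outcome points towards outcome-specific work, but the categories given are defined by surveys completed. The SAP also calls parenting attitudes secondary, so that outcome may fall outside the promise. For co-parenting and the two partner measures, only item missingness removes further follow-up respondents, and its extent is not given.

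Finally, full reversal of retention is an extreme assumption. The arms attend the standard workshops together (Protocol 7) and data collection does not differ by arm (Protocol 10.3). The SAP plans a Bonferroni correction and six outcomes, so the 0.05 error rates alone would overstate the consequence. These limits stand.

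**Conclusion.** The point holds as a gap in specification: no stated check compares the arms' characteristics among the fathers analysed for a given outcome. It holds whether the equivalence tests use all fathers at entry or the impact study sample.

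The size of any bias is unknown. The 0.07 to 0.11 SD, and the error of 22 to 41% at 0.05 or 7 to 17% at 0.05/6 (nominal 0.83%), rest on assumed opposite-direction attrition, an assumed trait effect and no adjustment for the trait. It would be tempting to conclude that the trial's estimates will be biased or its error rate inflated. The documents give no retention by characteristic and arm, so the figures show only that the specified non-response checks could miss such a bias. The change is worth making because it is cheap and serves the section's own aim.

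**What to change.** For each outcome, the SAP should:

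- (a) define analysed versus not analysed by that outcome's own sample rule, using the exit survey for parenting attitudes;
- (b) tabulate the characteristics already listed in the non-response section, plus the outcome's baseline score, by arm and analysed status;
- (c) run the baseline comparison by arm in that outcome's analytic sample and report standardised differences;
- (d) include the outcome's baseline score as a covariate whatever the test result, and add other characteristics imbalanced in that sample through the existing covariate rule.

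Step (d) should not rest on significance alone: at 310 per arm a test misses a 0.2 SD baseline gap about 30% of the time, and the milder case above more than half the time.

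The cost is SAP wording and more tables from data already held in nFORM and OLLE. Covariates may differ slightly between outcomes, which adds some analytic flexibility, so the imbalance rule should be fixed before outcome data are examined.
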